6.2.1.5 Dosage Adjustments, Delays, Rules for Withholding or Restarting, Permanent Discontinuation

Dosage Adjustments

The subject should continue on the same dose of AMG 224 throughout the study unless the following events occur:

- For subjects experiencing an adverse event meeting the DLT definition or intolerable related adverse events BUT showing evidence of response, there will be an option to reduce the dose to the immediate next lower dose level (ie Dose Level -1 as outlined in [Table 3](#) or a further lower dose level (ie Dose Level -2 as outlined in [Table 3](#)).
- The study drug can be resumed once the adverse events recover to baseline or Grade 1 and the reintroduction of AMG 224 is deemed safe by the Investigator, Amgen's Medical Monitor, and Global Safety Officer.
- Subjects must be informed of the risk of continuing on therapy. Each subject is only allowed a single dose reduction.
- For subjects experiencing thrombocytopenia after the DLT-window, there will be an option to reduce the dose to the immediate next lower dose level (ie, Dose Level -1 as outlined in [Table 3](#)) or a further lower dose level (ie Dose Level -2 as outlined in [Table 3](#) in the dose expansion part of the study (as described in [section 6.3.1](#)).

The investigator should notify Amgen immediately before administration of the lower dose of AMG 224.

Subject who have been dose-reduced will have an option to receive the higher dose (ie, Dose Level -1 or Dose Level 1) at the next planned cycle if the adverse event resolves to \leq grade 1 or baseline and the reintroduction of AMG 224 at the higher dose is deemed safe by the Investigator.

For dose reduction level, refer to [Table 3](#):

Table 3. Dose Reduction of AMG 224 for Toxicity (Only in Dose Expansion)

Dose level	Dose IV Q3W
Dose Level 1	
Dose Level -1	
Dose Level -2	

Subjects should not be rechallenged with AMG 224 if the following AMG 224-related adverse events occur:

- Any life-threatening adverse events
- DILI (Drug Induced Liver Injury) meeting Hy's law

- Persistent grade 3 adverse events that do not recover to baseline or Grade 1 within 4 weeks. Any treatment-related adverse event meeting DLT-criteria that recurs

Dosage Delays

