During the DLT-window, if the dosing is delayed for more than 7 days the subject will be removed from the study and will be replaced. After DLT-window, if the dosing is delayed for ≤ 3 weeks, the subject should resume the treatment as soon as possible if deemed safe by the investigator. The investigator should inform the Amgen Clinical team as soon as the unexpected dosing interruption occurs. If the dosing of AMG 224 is delayed more than 3 weeks (missing 1 cycle) due to treatment-related adverse events, the subject will be removed from the study. If the dosing delay occurred under conditions other than those associated with AMG 224 related toxicities, the case will be reviewed by Amgen medical monitor to determine whether the subject will be allowed to resume AMG 224 treatment.

Rules for Withholding or Restarting

AMG 224 should be withheld for any of the following:

- Suspected DLT (including AE that meet DLT definition outside DLT window)
- Grade 3 thrombocytopenia (follow the thrombocytopenia management in [Section 6.3.1](#))
- Aspartate aminotransferase (AST) or alanine aminotransferase (ALT) greater than 3x ULN or total bilirubin greater than 1.5x ULN

AMG 224 dosing can be resumed if the toxicities resolve to grade ≤ 1 or return to subjects' baseline values. The restarting of therapy should be deemed safe by the investigators and Amgen's medical monitor.

Rules for Permanent Discontinuation

Subjects will permanently discontinue from the investigational product if:

- Subjects experience adverse events meeting the DLT criteria at any time. Subjects will be followed until the DLT is resolved, returns to baseline value or is considered stable. Subjects will be withdrawn from AMG 224 treatment and will be treated as deemed appropriate by the investigator or treating physician. Except for:
 - Subjects showing evidence of response or subjects who in the opinion of the investigator may be responding to AMG 224, may have the option to continue therapy once the adverse events recover to baseline or Grade 1 and the re-introduction of AMG 224 is deemed safe by the investigator, Amgen's medical monitor, and Global Safety Officer. The subject should

restart at a reduced dose (see [Section 6.2.1.4](#)) subsection Dose Adjustments).

- Intolerability of the study treatment
- The dosing is delayed > 3 weeks due to AMG 224-related adverse events
- Disease progression according to IMWG response criteria
- Clinical significant deterioration of health status

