6.2.1.6 Dosage Limiting Toxicities

The grading of adverse events will be based on the guidelines provided in the Common Terminology Criteria for Adverse Events (CTCAE) version 4.0 (available online at <http://evs.nci.nih.gov/ftp1/CTCAE/About.html>). Determination of the severity of adverse events will be consistent with Common Terminology Criteria for Adverse Events (CTCAE) version 4.0. The relationship of an adverse event to investigational product will be determined by the Investigator. An event should be considered related to treatment if, in the Investigator's medical judgment, there is a reasonable possibility that the event may have been caused by AMG 224.

A DLT is defined as a Grade 3 or higher non-hematological or a Grade 4 hematologic adverse event that occurs during the DLT window (day 1 through day 28 after the administration of the first dose of AMG 224) in Part 1 Dose Exploration unless clearly attributable to causes other than AMG 224 treatment. DLT toxicities do not include fatigue, nausea, diarrhea, vomiting, neutropenia, anemia, thrombocytopenia and lymphopenia, increased serum creatinine or electrolytes abnormalities that are not clinically significant and require no treatment unless the following criteria are met:

Hematological toxicity:

- Grade 4 neutropenia lasting > 7 days
- Grade 3 or 4 neutropenia with fever > 38.5°C
- Grade 3 thrombocytopenia with ≥ Grade 2 hemorrhage
- Grade 4 thrombocytopenia lasting > 7 days
- Grade 3 anemia with symptoms or required intervention (eg, transfusion)
- Grade 4 anemia
- Lymphopenia of any grade is not considered a DLT

Approved

Non-hematological toxicity:

- \geq Grade 3 nausea, vomiting or diarrhea persisting more than 3 days despite optimal medical support
- Grade 3 fatigue persisting > 7 days
- \geq Grade 3 acute kidney injury (creatinine >3 X baseline or > 4.0 mg/dL) lasting > 3 days
- Elevation of either AST or ALT according to the following criteria:
 - $> 8x$ ULN;
 - $> 5x$ ULN but $< 8x$ ULN for ≥ 2 weeks;
 - $> 5x$ ULN but $< 8x$ ULN and unable to adhere to enhanced monitoring schedule; or
 - $> 3x$ ULN with clinical signs or symptoms that is consistent with hepatitis (such as right upper quadrant pain/tenderness, fever, nausea, vomiting, jaundice, rash or eosinophilia ($> 5\%$)).
- TBIL $> 3x$ ULN

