Grade 3 (PLT <50 to $\geq 25 \times 10^9/L$)	Yes, don't administer AMG 224 until platelet count recovers to \leq Grade 2 ($\geq 50K$)	Upon recovery, administer AMG 224 at Dose Level 1 (██████████ Q3W)	Upon recovery, administer AMG 224 at the same dose level	Yes, if grade 3 platelet count decrease did not recover to at least grade 2
Grade 4 (PLT $< 25 \times 10^9/L$) and last ≤ 7 days	Yes, don't administer AMG 224 until platelet count recovers to \leq Grade 2 ($\geq 50K$)	Upon recovery, administer AMG 224 at Dose Level -1 (██████████ Q3W) if deemed safe by the investigator	Upon recovery, administer AMG 224 at one lower Dose Level (minimum ██████████ Q3W) if deemed safe by the investigator	Yes, if grade 4 platelet count decrease did not recover to at least grade 2 OR subsequent drops in platelet count to Grade 4 after dose reduction

Approved

Table 4. Dosing Guideline Based on Platelet Count After 2nd Cycle

Grade of Platelet Count Decrease	Withhold Dose	Previous dose	Previous dose	Dose Discontinuation
Grade 3 or 4 PLT count decreased associated with < grade 2 bleeding	Yes, don't administer AMG 224 until platelet count recovers to ≤ Grade 2 (≥ 50K) and bleeding is controlled	Upon recovery, administer AMG 224 at Dose Level -1 (██████████) Q3W) if deemed safe by the investigator	Upon recovery, administer AMG 224 at one lower Dose Level (minimum ██████████ Q3W) if deemed safe by the investigator	Yes, if grade 3 or 4 platelet count decrease did not recover to at least grade 2 and bleeding is not controlled OR subsequent episode of Grade 3 or 4 thrombocytopenia associated with < grade 2 bleeding
Grade 4 (PLT < 25 10 ⁹ /L) and last > 7 days or Grade 3 or 4 (PLT < 50 10 ⁹ /L) with ≥G2 bleeding	N/A	N/A	N/A	Yes

Page 2 of 2

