9.1.2 Serious Adverse Events

A serious adverse event is defined as an adverse event that meets at least 1 of the following serious criteria:

- fatal
- life threatening (places the subject at immediate risk of death)
- requires in patient hospitalization or prolongation of existing hospitalization
- results in persistent or significant disability/incapacity
- congenital anomaly/birth defect
- other medically important serious event

An adverse event would meet the criterion of “requires hospitalization”, if the event necessitated an admission to a health care facility (eg, overnight stay).

If an investigator considers an event to be clinically important, but it does not meet any of the serious criteria, the event could be classified as a serious adverse event under the criterion of “other medically important serious event”. Examples of such events could include allergic bronchospasm, convulsions, blood dyscrasias, drug induced liver injury (DILI) (see [Appendix A](#) for DILI reporting criteria), or events that necessitate an emergency room visit, outpatient surgery, or urgent intervention.

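### In Part 2 after the 2nd cycle, the responder exception in Protocol 6.2.1.5 permits a reduced-dose restart after two platelet events for which Table 4 requires discontinuation, and no sentence says which applies

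*Protocol*

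**What the plan says.** **Protocol 6.2.1.5, Rules for Permanent Discontinuation.** AMG 224 stops when "Subjects experience adverse events meeting the DLT criteria at any time". Excepted are subjects with evidence of response and those who, in the investigator's opinion, "may be responding to AMG 224, may have the option to continue therapy once the adverse events recover to baseline or Grade 1". The investigator, medical monitor and Global Safety Officer must judge the restart safe, and the subject should "restart at a reduced dose". For the reduction, the text refers to 6.2.1.4, which holds the enrollment stopping rules; the dose-adjustment text is in 6.2.1.5.

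**Protocol 6.2.1.5, Dosage Adjustments, first bullet.** A subject with a DLT-type event and evidence of response may go to Dose Level -1 or -2 of Table 3. That table is marked as applying only in dose expansion.

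**Protocol 6.2.1.6.** The DLT criteria include "Grade 4 thrombocytopenia lasting > 7 days" and "Grade 3 thrombocytopenia with ≥ Grade 2 hemorrhage".

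**Protocol 6.3.1, Table 4.** This guides dosing by platelet count after the 2nd cycle. Its last row describes a Grade 4 count "and last > 7 days or Grade 3 or 4" counts with bleeding of at least Grade 2. The withholding column and both dose columns are marked not applicable, and the discontinuation column says yes. Response is not mentioned.

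**The concern.** The two DLT-type platelet events are the events in Table 4's last row. For the same Part 2 responder, one section offers a restart and the other ends treatment. A site that restarts can cite 6.2.1.5, and a site that stops can cite Table 4, so identical subjects could be handled differently with both sites claiming compliance.

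Section 2.4.2 names thrombocytopenia as the primary safety concern. At stake is whether a subject with prolonged Grade 4 platelets, or Grade 3 platelets with bleeding, is exposed again.

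**Working it through.** The plan gives no figure to reproduce. The check has three steps.

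**1. Do both texts reach the same subject?** The DLT definition in 6.2.1.6 names Part 1 and days 1 to 28. However, the stop rule in 6.2.1.5 applies at any time, and the matching Dosage Adjustments bullet uses Table 3 levels, which exist only in dose expansion. The exception is therefore live in Part 2, where Table 4 also applies.

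| Event, responder, Part 2, after 2nd cycle | 6.2.1.5 | Table 4, last row |
|---|---|---|
| Grade 4 platelets > 7 days | reduced-dose restart permitted after recovery to baseline or Grade 1 | discontinue |
| Grade 3 platelets with ≥ Grade 2 bleeding | same | discontinue |

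**2. Is there a rule of precedence?** Section 6.2.1.5 points to 6.3.1 twice: for the optional reduction when thrombocytopenia occurs after the DLT window, and for withholding at Grade 3. Section 6.2.1.1 cites both sections jointly. None of these ranks the exception against Table 4's discontinuation column.

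**3. Do the other bars already remove the overlap?**

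- *Life-threatening.* The no-rechallenge list includes "Any life-threatening adverse events". Section 9.1.2 explains the term as immediate risk of death, which a platelet count alone need not meet. Table 4 itself allows re-dosing after Grade 4 lasting 7 days or less. Even if every Grade 4 event were treated as life-threatening, Grade 3 with bleeding would remain.
- *Recurrence.* This spares a first event.
- *Timing.* Two limits apply: Grade 3 must recover to baseline or Grade 1 within 4 weeks, and dosing may not be delayed more than 3 weeks for related events. On a strict reading, the 4-week limit runs from onset and covers Grade 4 too. With a dose on cycle day 1, the next is due on day 1 + 21 = 22, and the delay limit is day 22 + 21 = 43. For onset on cycle day d (assumed 1 to 21), the last usable day is min(d + 28, 43).

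| Onset day d | Last usable day | Days left after an 8-day Grade 4 episode: last − (d + 8) | Days from onset, Grade 3 with bleeding: last − d |
|---|---|---|---|
| 1 | 29 | 20 | 28 |
| 15 | 43 | 20 | 28 |
| 21 | 43 | 14 | 22 |

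Eight days is the shortest whole-day episode exceeding 7 days. Each further day at Grade 4 removes one day from the third column. Recovery in time is therefore possible for both events.

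- *Judgment-based bars.* Thrombocytopenia that standard care cannot control (6.3.1), intolerability, and clinically significant deterioration (both 6.2.1.5) also stop treatment. They depend on the individual case, and a first event that resolves promptly need not trigger any of them.

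**The case against.** **Table 4 is the ordinary governing text.** Section 6.2.1.5 separates post-window thrombocytopenia from the general DLT-plus-response bullet and sends it to 6.3.1, which refers dose modification to Table 4. Amendment 4's rationale says that the thrombocytopenia dose adjustments were introduced for subject safety. This is good evidence of intent. It remains inference, because the pointers concern reduction and withholding, and the general bullet does not exclude platelet events.

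**The orders are not incompatible.** A reader might infer that a site cannot comply with both texts. It can: the exception is optional and needs agreement from three parties, and stopping satisfies both. Nor are decision-makers without a written rule, since Table 4's last row is one. What is missing is the sentence that closes the option.

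**The overlap may be nearly empty.** A reader might infer that any first event recovering in time clears every bar. The three judgment-based bars mean this cannot be asserted; the day counts show only that timing does not close the gap.

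**Further conflicts might be read in.** One candidate is the limit of one dose reduction per subject in 6.2.1.5, set against Table 4's stepwise reductions. The documents do not support this firmly. Amendment 4's rendering suggests that the limit belongs under the responder bullet, and the argument needs a column header that is redacted. Another candidate is that platelets should return to Grade 1 or baseline before any restart. The amendment log shows that this was the superseded rule and that Table 4's threshold of 50 × 10⁹/L replaced it.

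**Conclusion.** The point holds as an inconsistency in current text: 6.2.1.5 permits, for responders, a restart that Table 4 rules out. It covers two events, in Part 2, after the 2nd cycle. It should be fixed for subject safety.

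The number affected is likely small. Part 2 enrolls up to 20 subjects, and the gap needs a responder (or possible responder), a first qualifying event, prompt recovery and three-party agreement. The documents give no event rate, so no count can be stated.

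A reader might infer damage to the dose-finding result. The documents do not support that: Section 10.4.2.3 counts only DLTs inside the defined window in the primary analysis. If the 2nd cycle is taken as complete, Table 4 starts on schedule at study day 1 + 2 × 21 = 43, after the window ends on day 28. No effect on duration of response or time to progression is shown either.

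The conclusion assumes that the DLT criteria carry into Part 2 through the at-any-time wording and Table 3, and that a Grade 4 count alone is not automatically life-threatening. Without the second assumption, only Grade 3 with bleeding remains.

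**What to change.** 1. In 6.2.1.5, add to both the responder exception and the first Dosage Adjustments bullet: *This exception does not apply to events in the last row of Table 4.* If the medical team intends responders to be eligible after those events, write that into the row with its conditions.
2. Correct the exception's cross-reference from 6.2.1.4 to 6.2.1.5.
3. Minor clarification: the general restart rule in 6.2.1.5 requires Grade 1 or lower, or baseline, while Table 4 accepts 50 × 10⁹/L or more. Name thrombocytopenia after the 2nd cycle in Part 2 as the exception to that general rule, and keep Table 4's threshold.

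The cost is one sentence placed twice, one cross-reference and one clarifying sentence, after the medical team confirms its intent. These can go into the next amendment with a letter to sites. No visits, samples or subjects are added.

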Any subject meeting the criteria for Hy's Law case (ie, severe drug-induced liver injury) will be considered a DLT. A Hy's Law case is defined as: AST or ALT values of $\geq 3x$ ULN AND with serum total bilirubin level (TBL) of $> 2x$ ULN without signs of cholestasis and with no other clear alternative reason to explain the observed liver-related laboratory abnormalities (see [Section 6.4](#) for hepatotoxicity management and [Appendix A](#) for further explanation of Hy's law case and Management of Hepatic Function).

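### For a small group of unexplained, non-Hy's-law liver events, Protocol 6.2.1.5 and 6.4 set different standards for restarting AMG 224, and neither section is given precedence

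*Protocol*

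**What the plan says.** **Protocol 6.2.1.5** holds AMG 224 for a suspected DLT, for AST/ALT above 3x ULN, or for total bilirubin above 1.5x ULN. It then gives two ways back.

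- *Resume rule:* "AMG 224 dosing can be resumed if the toxicities resolve to grade" 1 or below, or to the subject's baseline, if the investigators and medical monitor think it safe.
- *Responder exception:* events meeting DLT criteria normally end treatment, but a responder or possible responder "may have the option to continue therapy once the adverse events recover to baseline or Grade 1". The dose is reduced, and the investigator, medical monitor and Global Safety Officer must judge it safe. Dosage Adjustments, in the same section, repeats the idea: "The study drug can be resumed once the adverse events recover to baseline or Grade 1". It also requires that the subject be told the risk.

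Neither route mentions an alternative cause. The no-rechallenge list in 6.2.1.5 has one liver-specific item, "DILI (Drug Induced Liver Injury) meeting" Hy's law. It also bars life-threatening events, Grade 3 events not recovered within 4 weeks, and recurrent related events meeting DLT criteria. A separate limit removes subjects whose related delay exceeds 3 weeks.

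**Protocol 6.2.1.6** defines Hy's law as AST/ALT at or above 3x ULN "AND with serum total bilirubin level (TBL) of" more than 2x ULN, without cholestasis or another clear reason. INR does not enter.

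**Protocol 6.4.1** withholds permanently when all of these hold: AST/ALT above 3x ULN from a baseline below ULN; bilirubin above 2x ULN or INR above 1.5; no other cause apparent. **6.4.2** frames its conditional holds as recommendations. It allows rechallenge to be considered if an alternative cause is found and values return to normal or baseline. **6.4.3** adds unanimous agreement of subject, principal investigator and sponsor. It says subjects who clearly meet permanent-discontinuation criteria, with no definite alternative cause, are never to be rechallenged.

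**The concern.** Hepatotoxicity is one of the toxicities that Protocol 2.3 anticipates for this linker and warhead, so restart after liver injury should have one answer. Here a site could follow 6.2.1.5 to the letter and re-expose a subject whom 6.4 keeps off drug. Two sites, or two sponsor reviewers, could decide identical cases in opposite ways while each complies with the protocol.

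The responder exception bears directly on this. The DLT definition removes events clearly due to another cause, so the hepatic DLTs that reach the exception are mostly the unexplained ones, which 6.4.2 would keep off drug.

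No endpoint or analysis is shown to be affected. What is at stake is a consistent safety rule for a few subjects.

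**Working it through.** There is no planned figure to reproduce. The check compares lists, applies both sections to defined cases, and tests whether the delay limits already remove the group.

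**1. Shared triggers.** Section 6.4.2 has 4 AST/ALT triggers + 1 bilirubin trigger (above 3x ULN) + 1 ALP trigger (above 8x ULN) = 6. The list in 6.2.1.6 that begins "Elevation of either AST or ALT according to the following criteria" has the same 4, and bilirubin above 3x ULN is also there: 4 + 1 = 5 of 6 shared. In 6.4.1 the second criterion has 2 alternatives, bilirubin or INR. Hy's law covers only bilirubin, so 1 of 2 (INR) is outside the bar in 6.2.1.5. These are counts of list items, not of patients.

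**2. Cases.** In each, no other cause is apparent, baseline AST/ALT is below ULN, recovery is within the delay limits, and the event is neither life-threatening nor recurrent.

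| Case | Under 6.2.1.5 | Under 6.4 | Result |
|---|---|---|---|
| A. Responder, ALT 9x ULN, normal bilirubin and INR | Reduced-dose restart possible | 6.4.2 asks for an alternative cause | Differ |
| B. Responder, not Hy's law: ALT between 5x and 8x ULN for 2 weeks or more, or above 3x with hepatitis symptoms, or bilirubin above 3x | Reduced-dose restart possible | As A | Differ |
| C. ALT 4x ULN, INR 1.6, bilirubin 1.2x ULN, no symptoms | Hold, then resume on recovery; Hy's law bar not met | Permanent hold (6.4.1) | Differ |
| D. ALT 4x ULN, bilirubin 2.5x ULN, no cholestasis | Barred (Hy's law) | Permanent hold (6.4.1) | Agree |
| E. ALT 4x ULN alone, no symptoms | Hold, then resume | No 6.4.1 or 6.4.2 trigger | No conflict |

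Case C does not depend on how binding 6.4.2 is. Cases A and B do.

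**3. Delay limits.** One limit reads "If the dosing of AMG 224 is delayed more than 3 weeks (missing 1 cycle) due to treatment-related adverse events", and removal follows; in the DLT window the limit is 7 days.

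- Longest gap between doses in the DLT window: 21 + 7 = 28 days.
- Longest gap afterwards: 21 + 21 = 42 days.
- Slowest shared trigger (AST/ALT between 5x and 8x ULN for at least 2 weeks): 14 days.
- Four-week limit for Grade 3 events: 28 days, assumed to run from onset.
- Time left to recover: min(28, 28) − 14 = 14 days in the window; min(42, 28) − 14 = 14 days after it.

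Fourteen days is a ceiling, but it shows that the limits shrink the group without emptying it.

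**4. Precedence.** The nearest link is a pointer in 6.2.1.6 to Section 6.4 "for hepatotoxicity management and" Appendix A. It sits in the Hy's law paragraph, where the sections agree, and ranks neither. In the hold list of 6.2.1.5 the thrombocytopenia item refers to 6.3.1; the hepatic item has no such reference to 6.4. The bar in 6.4.3 cites 6.2.1.4 for its criteria, but 6.2.1.4 holds only enrollment stopping rules. The responder exception makes the same mis-citation when it refers to dose adjustments.

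**The case against.** The strongest reply has four parts.

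*Section 6.4 is the dedicated hepatotoxicity section, and a permission does not override a prohibition.* A site that reads both sections can satisfy both by following 6.4. That is the natural reading, but it stays an inference because nothing instructs it.

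*Appendix A fills the gap.* It requires close observation and an investigation of alternative causes for AST/ALT above 3x ULN. Concurrent transaminase elevation with bilirubin and/or INR elevation, by the 6.4 criteria, must reach the sponsor as a serious adverse event within 24 hours. This stands. A reader might infer that causes go uninvestigated or that a subject could restart unreviewed; the documents do not support that, because both restart routes also need the medical monitor. What Appendix A does not do is make restart depend on the result of the work-up. It also asks for at least 4 weeks of close observation after discontinuation. Whether a hold counts as discontinuation is not stated, and the 14-day figure ignores this.

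*6.4.3 already bars unexplained cases, and its wrong citation can be decoded.* Partly so: the intended target is probably 6.2.1.5. But that section contains the responder exception, and 6.4.3 does not say whether the exception survives.

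*The group is small, and the fix is a clinical choice.* Both stand and limit the weight of the point.

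**Conclusion.** The point holds in a limited form. The INR route (case C) and the two wrong cross-references are its firmest parts. The responder route (cases A and B) is softer because 6.4.2 only recommends.

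The affected events are unexplained, outside Hy's law, not life-threatening or recurrent, and recovered within the delay limits. A reader might infer that 6.2.1.5 opens restart after any unexplained liver injury. It does not: its own list bars Hy's law, life-threatening, persistent Grade 3 and recurrent DLT-type events, and cases D and E show no conflict.

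The size is 5 of 6 shared triggers in 6.4.2 and 1 of 2 uncovered alternatives in 6.4.1. The documents give no hepatic event rate, so no number of subjects can be stated. The recovery arithmetic assumes that the 4-week limit runs from onset. The wording should be corrected, because it can permit re-exposure that another section forbids.

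**What to change.** 1. Add to the no-rechallenge list in 6.2.1.5: events meeting ALL criteria in 6.4.1, including the INR above 1.5 route. The word ALL matters. A version triggered by any single criterion would permanently bar subjects with isolated AST/ALT above 3x ULN.
2. Add to both the hepatic hold item and the responder exception in 6.2.1.5: for events meeting all criteria in 6.4.1, or any trigger in 6.4.2, Section 6.4 governs restart; other holds for AST/ALT above 3x ULN or bilirubin above 1.5x ULN follow 6.2.1.5.
3. In the responder exception, correct the reference to 6.2.1.5, Dosage Adjustments. In 6.4.3, correct it to 6.4.1 and the permanent-discontinuation rules of 6.2.1.5, and state that the responder exception does not apply to unexplained hepatic events.

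The cost is a protocol amendment with IRB/IEC approval. There is also a clinical price: a few responders with unexplained liver toxicity, all after at least 3 prior lines, lose the option to restart. Item 2 makes the recommendation in 6.4.2 the governing rule, so the sponsor should adopt it as a deliberate decision and not as an editorial correction.
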